5.5 Sample storage procedures

All samples will either be analysed within 3 days of collection to minimize the chance of degradation, or stored at -80 degrees C until analysis. After analysis, all samples will be destroyed in accordance with the Human Tissue Act.

6. Safety measures

The safety of trial subjects will precedence over any other aspect of the trial. Consequently, prior to the initiation of laboratory work, lines of communication will be established with the study sponsor, to ensure that any issues that may impact on patient safety are reported without delay. These may include, but are not limited to, the reporting of unexpected or out of range results and significant deviations from the clinical protocol or work instructions.

6.1 General Definitions

Instructions for Safety Reporting (Research other than CTIMPs)

In other research other than CTIMPs, a serious adverse event (SAE) is defined as an untoward occurrence that:

- (a) Results in death;
- (b) Is life-threatening;
- (c) Requires hospitalisation or prolongation of existing hospitalisation;
- (d) Results in persistent or significant disability or incapacity;
- (e) Consists of a congenital anomaly or birth defect; or is otherwise considered medically significant by the investigator.

An SAE occurring to a research participant should be reported to the main REC where in the opinion of the Chief investigator the event was:

- **Related** – that is, it resulted from administration of any of the research procedures, and
- **Unexpected** – that is, the type of event is not listed in the protocol as an expected occurrence.

Serious Adverse Events Procedures General Definitions

An adverse event (AE) is any untoward medical occurrence in a participant which does not necessarily have a causal relationship with the study intervention and can include;

- any unintentional, unfavourable clinical sign or symptom
- any new illness or disease or the deterioration of existing disease or illness
- any clinically relevant deterioration in any laboratory assessment or clinical tests

6.2 Notification and reporting Adverse Events or Reactions

[figure not shown]
Expected AE AR/SAEs and SARs Not reportable

If the AE is not defined as SERIOUS, the AE is recorded in the study file and the participant is followed up by the research team. The AE is documented in the participants' medical notes (where appropriate) and the CRF.

For the purpose of the research study, adverse events related to the study are limited to those involved with sample collection. Blood sampling will involve an invasive blood test which has the attendant risks of pain, local bruising and infection. These risks will be minimised as blood sampling will be done by experienced practitioners using aseptic technique.

6.3 Notification and Reporting of Serious Adverse Events

Instructions for Safety Reporting (Research other than CTIMPs)

6.4 Urgent Safety Measures

The CI may take urgent safety measures to ensure the safety and protection of the clinical trial subjects from any immediate hazard to their health and safety, in

accordance with Regulation 30. The measures should be taken immediately. In this instance, the approval of the Licensing Authority Approval prior to implementing these safety measures is not required. However, it is the responsibility of the CI to inform the sponsor and Main Research Ethics Committee (via telephone) of this event **immediately**.

The CI has an obligation to inform both the Main Ethics Committee **in writing within 3 days**, in the form of a substantial amendment. The sponsor (ABM University LHB through its Research and Development Office) must be sent a copy of the correspondence with regards to this matter.

6.5 Annual Safety Reporting

The CI will send the Annual Progress Report to the main REC using the NRES template (the anniversary date is the date on the MREC “favourable opinion” letter from the MREC) and to the sponsor.

6.6 Overview of the Safety Reporting Process responsibilities

The CI/PI has the overall safety reporting responsibility. The CI/PI has a duty to ensure that monitoring and reporting is conducted in accordance with the sponsor’s requirements.

7. Statistical Considerations

7.1 Sample Size

1,800 patients will be included in the study to provide a representative number in each subgroup for the purposes of this study.

Based on analysis from our pilot data (currently at n=200) the 300 samples per subgroup are predicted to provide the required independent validation test set to achieve over 85% sensitivity and specificity with 80% power at the 95% confidence interval.

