**TITLE OF THE PROTOCOL: RAMAN SPECTROSCOPY AND
COLORECTAL CANCER: TOWARDS EARLY DIAGNOSIS AND
PERSONALISED MEDICINE**

Short title/Acronym: Raman spectroscopy and colorectal cancer

Sponsor:

Representative of the Sponsor:

[name]
R&D Manager
R&D Department
Morriston Hospital
Swansea
[name]

REC reference: 14/WA/0028

STUDY SUMMARY/SYNOPSIS

TITLE	Raman spectroscopy and colorectal cancer: towards early diagnosis and personalised medicine
SHORT TITLE	Raman spectroscopy and colorectal cancer
Protocol Version Number and Date	ABM/RS/v4 Version 4;08/2/2017
Methodology	Prospective cohort observational study
Study Duration	5 years 6 months
Study Centre	ABM University LHB and Swansea University
Objectives	To explore the feasibility of detecting presence of differing stages of colorectal cancer at different phases of treatment using Raman spectroscopy
Number of Subjects/Patients	1,800 across 8 study groups
Main Inclusion Criteria	Stage T3/4 colorectal cancer (group 1) n=300 T1/2 early colorectal cancer (T1/2) from Bowel Screening Wales programme (group 2) n=300 Benign colorectal polyps (>1cm size)(group 3) n=200 Matched controls (without history of inflammatory bowel disease or familial bowel cancer)(group 4) n=300 Locally advanced rectal cancer requiring chemoradiotherapy (group 5) n=80 Bowel cancer patients at high risk of developing metastatic disease (group 6) n=20 Patients diagnosed with other cancer types (e.g. lung, pancreas)(group 7) n=300 Patients in primary care with colorectal symptoms (group 8) n=300
Statistical Methodology and Analysis	Principal Components Analysis (PCA) and hierarchical cluster analysis to measure accuracy, sensitivity and specificity measures for each patient group.

Protocol Agreement Page

The clinical study as detailed within this research protocol (**Version 2, dated 9th May 2014**), or any subsequent amendments will be conducted in accordance with the Research Governance Framework for Health & Social Care (2005), the World Medical Association Declaration of Helsinki (1996) and the current applicable regulatory requirements and any subsequent amendments of the appropriate regulations.

Chief Investigator Name: [name] [name] (Consultant Surgeon)

Chief Investigator Site: Singleton Hospital, Swansea

Contact details: [contact]
 Email: [contact]
 Fax:

Signature and Date:

Statistician Name: [name], Swansea Trials Unit

Contact details: Tel No:
 Email:[contact]
 Fax:

Signature and Date:

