Towards utilising the blood test as a means of discriminating between patients with colorectal cancer and those without we wish to obtain blood samples from 300 patients in primary care with colorectal symptoms and compare the test result (positive, equivocal or negative) with their final diagnosis (colorectal cancer or benign pathology). The blood test results will not be revealed to the GP or the patient so cannot influence the current referral pathway until the blood test is validated for this patient population. We will use this data to plan a subsequent interventional study.

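### The 80% power claimed in section 7.1 cannot hold for sensitivity in group 8, and cannot be verified for the groups that do have 300 of one class

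*Protocol*

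**What the plan says.** The second paragraph of Protocol section 7.1 is the only quantitative justification of the sample size. It says that "300 samples per subgroup are predicted to provide the required independent validation test set to achieve over 85% sensitivity and specificity with 80% power". The confidence level is put at 95%. The stated source is the pilot: "Based on analysis from our pilot data (currently at n=200". No pilot sensitivity or specificity is given, and 7.1 does not say whether 85% is the expected value, the observed value or a lower limit to be exceeded.

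The synopsis and section 3.1 put 300 patients in each of groups 1, 2, 4, 7 and 8. The others are smaller: "Benign colorectal polyps (>1cm size)(group 3) n=200", "Locally advanced rectal cancer requiring chemoradiotherapy (group 5) n=80", and 20 in group 6.

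Group 8 differs in kind from the other groups of 300. Section 3.1 plans to "obtain blood samples from 300 patients in primary care with colorectal symptoms" and to compare the test result with a final diagnosis that may be cancer or benign. Under section 3.2 these patients enter on symptoms rather than histology, and under section 4.2 the GP identifies them when they first present.

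**The concern.** Sensitivity is estimated only in patients who have the cancer, and specificity only in those who do not. Groups 1 and 2 are all cancers and group 4 is all controls, so 300 there is the right denominator for one measure. In group 8 the 300 is split between the two, so it cannot be the denominator of both, and the cancer share is likely to be the small one.

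This matters because section 3.1 says the group 8 data will be used to plan a later interventional study. A reader who takes 7.1 at face value would treat the group 8 sensitivity, and so the rate of missed cancers, as backed by 300 observations and 80% power.

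A second problem concerns the groups where 300 is the right denominator. A power figure needs both a bound and an assumed true value, and 7.1 supplies one number.

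**Working it through.** **Inputs.** From 7.1: n = 300, 85%, 80% power, 95% confidence. From the synopsis and 3.1: group sizes 300, 300, 200, 300, 80, 20, 300, 300, which sum to 1,800 as stated. Assumed here because the protocol does not say: 85% is the bound to exclude, an exact (Clopper-Pearson) two-sided 95% interval is used, and colorectal cancer prevalence in group 8 is 1% to 10%.

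**Can the plan's own figure be reproduced?** Not from its inputs, because the second proportion is missing. With p0 = 0.85 and true value p1, the normal approximation is

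n = [(1.96·√(p0(1−p0)) + 0.8416·√(p1(1−p1))) / (p1 − p0)]².

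At p1 = 0.905: (1.96 × 0.3571 + 0.8416 × 0.2932) / 0.055 = 17.21, and 17.21² ≈ 296, close to 300. Other added assumptions also fit:

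- one-sided 5% with a true value of 90%: exact power 80.9%;
- an expected 85% against a null of 78.5%: exact power 81.4%.

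So 300 is compatible with several designs, and 7.1 does not say which one was meant.

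**300 of one class, bound 85%.** 267/300 gives a lower limit of 84.9% and 268/300 gives 85.3%, so at least 268 correct (89.3%) are needed. Exact power is P(X ≥ 268 | n = 300, p):

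| True value | Power |
|---|---|
| 88% | 27% |
| 90% | 69% |
| 90.5% | 79% |
| 90.6% | 80% |
| 91% | 87% |

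**Group 8 sensitivity.** The number of cancers is 300 × prevalence: 3 at 1%, 9 at 3%, 15 at 5%, 30 at 10%.

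- *Perfect test.* With all n cancers detected the lower limit is 0.025^(1/n). It is 84.6% at n = 22 and 85.2% at n = 23. At least 23 cancers are therefore needed, a prevalence of 23/300 = 7.7%, before any result can exclude 85%.
- *30 cancers.* 29/30 gives a lower limit of 82.8%, so all 30 must be detected. Power at a true 95% is 0.95^30 = 21%.
- *Precision.* 8/9 detected gives an exact interval of 52% to 99.7%; 13/15 gives 60% to 98%; 26/30 gives 69% to 96%.
- *Lenient reading (expected 85% against 78.5%).* 15/15 has a lower limit of 78.2% and still fails. With 30 cancers, 29 must be detected, and power at a true 85% is about 5%.
- *Beyond the assumed range.* Power of 80% at a true 95% first appears at about 75 cancers, a prevalence of 25%. Conversely, 300 cancers would take 3,000 patients at 10% and 30,000 at 1%.

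**Group 8 specificity.** The non-cancers number 270 to 297 over the same range, close to 300. An observed 85% has an exact interval of about 80% to 89% at either end.

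**Smaller groups.** With bound 85%, 80% power needs a true value of about 91.9% at n = 200 and 95.1% at n = 80. At n = 20 a perfect score has a lower limit of 83.2%.

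**The case against.** The strongest reply is that 7.1 promises performance over 85%, not performance of exactly 85%, and that 300 per class does give about 80% power if the true value is about 90.6%. The pilot may support such a value. This stands for group 1 or 2 against group 4: the claim there is unverifiable, not shown to be false.

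Three stronger readings are tempting, and the protocol does not support them.

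- *Power is negligible at a true 85%, so 300 is too few.* If 85% is the bound, the chance of success at a true 85% is the type I error. It is at most 2.5% at any sample size and says nothing about whether 300 is enough.
- *Sensitivity and specificity must both succeed, so joint power is lower still.* Section 7.1 sets no joint decision rule, and a joint figure would also assume independence.
- *Groups 3, 5 and 6 are underpowered against a promise made for them.* Section 7.1 can be read as covering only the groups of 300. Section 3.1 gives groups 5 and 6 serial-sampling aims. The synopsis does mention sensitivity and specificity for every group, but attaches no 85% target or power. This is mainly a wording inconsistency.

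It is also fair to say that 7.1 does not name group 8, that the prevalence is assumed here, and that the study is exploratory with group 8 results withheld from GPs and patients. None of this rescues the sensitivity claim. Group 8 is one of the groups of 300, and 300 mixed patients cannot supply 300 cancers and 300 non-cancers.

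**Conclusion.** Wrong as written, on a narrow ground. The stated power does not hold for sensitivity in group 8 at any prevalence in the assumed 1% to 10%. Below 23 cancers no result can exclude 85%, and at 30 cancers power is 21% even at a true 95%. The failure does not depend on treating 85% as the bound, since the lenient reading fails too. It does depend on prevalence staying well below about 25%, which the protocol neither states nor rules out. Group 8 specificity is close to the intended precision.

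For groups with 300 of one class the claim is incomplete. It is attainable for each measure separately if the true value is about 90.6% and 85% is the bound, but 7.1 says neither. The study's total and its group sizes are not shown to be inadequate. Because the study is exploratory, its primary objective is an association, and the remedy is rewording, this ranks below a must-fix.

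**What to change.** Restate the second paragraph of section 7.1:

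- (a) Limit the power claim to groups with 300 of one class, and say which measure each informs: groups 1 and 2 for sensitivity, group 4 for specificity, and group 7 for specificity against other cancers. Apply it to each measure separately. State the bound and the assumed true value. If the bound is 85% with an exact two-sided 95% interval, the true value must be about 90.6%; if another design was intended, give the sponsor's pilot-based values.
- (b) For group 8, say that specificity will have similar precision (about 270 to 297 non-cancers under an assumed 1% to 10% prevalence). Sensitivity will be reported with an exact 95% interval on the cancers found, with no power claimed.
- (c) Claim no diagnostic power for groups 3, 5 and 6, and drop the wording that implies 300 in every subgroup.

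The cost is one paragraph and a less favourable stated figure. No patients or procedures are added.

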7.2 Statistical Analysis

Statistical analysis and feasibility: The spectral analysis will be conducted using in-house principle component analysis (PCA) tools. This type of analysis is excellent for discriminating subtle spectral differences and determining commonality within datasets. The key aspect here will also include using the principle component loadings to ascertain the origin of the spectral differences, i.e. linking the spectral changes to macromolecular changes in the samples. Specially, by combining principal component analysis and hierarchical cluster analysis, the statistical difference between Raman spectra of different patient groups can be revealed effectively leading to specific accuracy, sensitivity and specificity measures. The research will also consider the development of PCA-based algorithms to establish calibration PCA loadings which can be run against ‘unknown’ samples. These new tools will enable the development of a

diagnosis platform and hence establish the route towards early diagnostics and personalised medicine.

8. Data Handling & Record Keeping

8.1 Confidentiality

Samples will be pseudoanonymised with a unique participant study number for the purposes of analysis. This number will be used on all CRFs and study forms. A file listing the unique participant study number and patient hospital number will be maintained on a password protected NHS computer accessible only by the Principal Investigator. The study sponsor (NHS R&D department) will have access to study data for monitoring purposes. Participants consent will be sought to permit this access.

8.2 Study Documents

- A signed protocol and any subsequent amendments
- Current/Superseded Patient Information Sheets (as applicable)
- Current/Superseded Consent Forms (as applicable)
- Indemnity documentation from sponsor
- Conditions of Sponsorship from sponsor
- Conditional/Final R&D Approval
- Signed site agreement
- Ethics submissions/approvals/correspondence
- CVs of CI and site staff
- Delegation log
- Staff training log
- Patient identification log
- Enrolment log
- Protocol training log
- Correspondence relating to the trial
- Communication Plan between the CI/PI and members of the study team

8.3 Record Retention and Archiving

During the course of research, all records are the responsibility of the Chief Investigator and will be kept in secure conditions in a pseudoanonymised manner in either a locked filing cabinet in a locked office in the case of paper records, or on a password protected secure computer in the case of digital records. When the research trial is complete, records will be kept for a further 5 years as per local R&D guidelines. Archiving is provided by Transmedia, ABMU's archive facility. The R&D department keeps a log of all archiving activity.

8.4 Compliance

The CI will ensure that the trial is conducted in compliance with the principles of the Declaration of Helsinki (1996), and in accordance with all applicable regulatory requirements including but not limited to the Research Governance Framework, Trust and Research Office policies and procedures and any subsequent amendments. Similarly all procedures, handling and disposal of human tissue will be in accordance with the principles laid out in the Human Tissue Act.

8.5 Clinical Governance Issues

8.5.1 Ethical Considerations

This protocol and any subsequent amendments, along with any accompanying material provided to the patient in addition to any advertising material will be submitted by the Investigator to the South West Wales Research Ethics Committee.

8.6 Quality Control and Quality Assurance

7.6.1 Summary Monitoring Plan

The Co investigators will establish quality control. The co-investigators will monitor protocol deviations, with the Chief investigator assuming overall responsibility.

